### **7.3.3 Safety analyses**

Safety will be assessed for the endpoints listed in [Section 5.2.1](#). All treated subjects (that is, all subjects who received at least one dose of study drug), will be included in the safety evaluation. Safety analyses will be descriptive in nature and will be based on BI standards.

The analyses will be done by 'treatment at onset'.

Treatments will be compared in a descriptive way. Tabulations of frequencies/proportions will be used for the evaluation of categorical (qualitative) data, and tabulations of descriptive statistics will be used to analyse continuous (quantitative) data.

Measurements (such as ECG, vital signs, or laboratory parameters) or AEs will be assigned to treatments (see [Section 4.1](#)) based on the actual treatment at the planned time of the measurement or on the recorded time of AE onset (concept of treatment emergent AEs).

Therefore, measurements planned or AEs recorded prior to first intake of trial medication will be assigned to 'screening', those between first trial medication intake until end of the residual effect period (see [5.2.2.2](#)) will be assigned to the treatment period. Events after the residual effect period but prior to end of trial examination will be summarized as 'follow-up'. These assignments including the corresponding time intervals will be defined in detail in the TSAP.

Adverse events will be coded using the Medical Dictionary for Regulatory Activities (MedDRA). Frequency, intensity and causal relationship of AEs will be tabulated by treatment, primary system organ class and preferred term. SAEs and other significant AEs (according to ICH E3), and AESIs will be listed separately (see [Section 5.2.2.1](#)).

Laboratory data will be compared to their reference ranges. Values outside the reference range will be flagged. Additionally, differences from baseline (Day 1 of period 1) will be evaluated.

For vital signs, the differences from baseline will be evaluated.

Relevant ECG findings will be reported as AEs.

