6. GENERAL ANALYSIS DEFINITIONS

6.1 TREATMENT(S)

For basic study information on investigational products, assignments of treatment, and selection of doses, please see CTP, Sections 3 and 4. For details of dosage and formulation see Table 6.1: 1 below.

Table 6.1: 1 Labels for treatments for use in the CTR

Treatment	Substance	Formulation	Unit strength	Dosage	Short label
R1 (Reference 1)	BI 409306	Film coated tablet	25 mg	1 tablet on Day 29	BI
T1 (Test 1)	BI 409306 Microgynon®	Film coated tablet Coated tablet	25 mg 0.03 mg EE / 0.15 mg LNG	1 tablet on Day 18	BI+Microgynon®
R2 (Reference 2)	Microgynon®	Coated tablet	0.03 mg EE / 0.15 mg LNG	1 tablet on Day 17	Microgynon®
T2 (Test 2)	Microgynon® BI 409306	Coated tablet Film coated tablet	0.03 mg EE / 0.15 mg LNG 25 mg	1 tablet on Day 18	BI+Microgynon®

The following separate study phases will be defined for the analyses of AEs:

- Screening (ranging from day of informed consent until first administration of study drug)
- Microgynon® treatment (ranging from the time of first intake of Microgynon® until the time of first administration of BI 409306 or last intake of Microgynon® + Microgynon® REP (10 days), whatever occurs earlier)
- BI 409306 + Microgynon® treatment (ranging from the first administration of BI 409306 + Microgynon® until end of Microgynon® REP (10 days))
- BI 409306 treatment
- Follow up BI 409306 treatment

The residual effect period (REP) for BI 409306, when measurable drug levels or PD effects are still likely to be present, The REP for Microgynon® is considered to be 10 days.

Displays of AEs will be presented separately for the following treatments during on treatment phase:

- BI 409306, tablet, qd (labelled "BI")
- Microgynon®, tablet, qd (labelled "Microgynon")
- BI 409306, tablet, qd + Microgynon®, tablet, qd (labelled "BI + Microgynon")

Two types of AE displays will be provided in the report:

A) Section 15.3 and Appendix 16.1.9.2.8 (for ClinicalTrials.gov) of the CTR displays:

In these displays, the on treatment phase will be analysed (labelled with the name of the study treatment (short label)). Screening and Follow-up BI will not be included in this analysis.

The following total will be provided in addition (Section 15.3 only):

- a total over all on treatment phases involving BI ("Total BI")
- a total over all on treatment phases included in this analysis ("Total on treatment")

B) Section 15.4 and Appendix 16.1.9.2.8 (except for ClinicalTrials.gov) of the CTR displays:

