- Screening
- On treatment (labelled with the name of the study treatment (short label))
- Follow-up BI (labelled "FU BI")

In Section 16.1.9.2.8 AE tables, the following totals will be provided in addition:

- a total over all study phases ("Total")

Tables of vital signs and laboratory values will present results by the following separate study phases which will be defined for the analyses of vital signs and laboratory values:

- Screening (ranging from day of informed consent until first administration of study drug)
- Microgynon® treatment (ranging from first intake of Microgynon® until first administration of BI 409306 or last intake of Microgynon® + Microgynon® REP (10 days), whatever occurs earlier)
- BI 409306 + Microgynon® treatment (ranging from first administration of BI 409306 + Microgynon® until administration of BI 409306 +)
- Microgynon® treatment (ranging from end of until last intake of Microgynon® + Microgynon® REP (10 days))
- BI 409306 treatment (ranging from first administration of BI 409306 alone until EOT or last intake of BI 409306 + whatever occurs earlier)

- Follow up BI 409306 treatment (ranging from end of last BI 409306 treatment +

For detailed information on the handling of the treatments in the O*C views refer to Technical TSAP analysis data set (ADS) plan.

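### SAP 6.1 lets the combined-treatment AE phase run to Day 31, so it takes in the first 48 h after the BI 409306-alone dose on Day 29

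*SAP*

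**What the plan says.** SAP Section 6.1 introduces its list of AE phases with "The following separate study phases will be defined for the analyses of AEs". Two bullets matter here:

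- The Microgynon phase runs "until the time of first administration of BI 409306 or last intake of Microgynon® + Microgynon® REP (10 days), whatever occurs earlier". It stops when the next treatment begins.
- The phase after it is "BI 409306 + Microgynon® treatment (ranging from the first administration of BI 409306 + Microgynon® until end of Microgynon® REP (10 days". It has no such stop.

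The list then names a BI 409306 phase and a BI 409306 follow-up phase. Their AE time limits are not visible, and neither is the length of the BI 409306 REP. Table 6.1: 1 of the SAP gives the Day 29 dose the short label BI.

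Protocol Section 5.2.2.2 sets the Microgynon REP at 10 days from the last Microgynon administration. Protocol Section 7.3.3 states the principle, "The analyses will be done by 'treatment at onset", and assigns AEs "based on the actual treatment at the planned time of the measurement or on the recorded time of AE onset". It leaves the boundaries to the SAP: "These assignments including the corresponding time intervals will be defined in detail in the TSAP".

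**The concern.** The combined phase stays open after a different treatment, BI 409306 alone, has been given. The protocol leaves the intervals to the SAP, so its general principle shows the intended direction but does not supply the missing boundary.

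At stake is how AEs are divided between the BI and BI + Microgynon columns. Subjects are in the trial site from Day 28 to Day 32, so the affected window is a closely observed part of the exposure to BI 409306 alone.

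The by-treatment columns also feed the ClinicalTrials.gov display. The SAP specifies the BI total and the on-treatment total for another section of the report only ("The following total will be provided in addition (Section 15.3 only"), so the registry display has no specified total beside the columns. SAP Section 7.2 uses the same phases to decide which treatment a medication is concomitant to, so the overlap carries into that assignment too.

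**Working it through.** **Inputs**

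- Combined dose: Day 18, 408:00 (Protocol 3.1 and Flow Chart).
- Last Microgynon dose: Day 21, 480:00 (same sources).
- BI 409306 alone (R1): Day 29, 672:00 (same sources).
- Microgynon REP: 10 days = 240 h from the last Microgynon dose (Protocol 5.2.2.2).
- Planned number of subjects: 16 (Protocol 7.6).

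The documents state no end day for the phase, so there is no figure of theirs to reproduce. The clock can be checked: hours = (day − 1) × 24 gives 408, 480 and 672 for Days 18, 21 and 29, as in the Flow Chart.

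**Overlap**

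- End of combined phase = 480 + 240 = 720:00, which is Day 31 at 09:00.
- Time after R1 inside the phase = 720 − 672 = 48 h.
- Length as written = 720 − 408 = 312 h, so the overlap is 48/312 = 15%.
- Length if cut at R1 = 672 − 408 = 264 h, with no overlap.

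**Sensitivity to the reading**

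- REP run to midnight at the end of Day 31: 720 + 15 − 672 = 63 h.
- Last Microgynon intake on Day 20 instead of Day 21: 24 h. On Day 19: 0 h.
- REP counted from Day 18: 408 + 240 = 648:00, before R1, so no overlap. This contradicts the protocol, which counts from the last Microgynon administration.

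**Effect on the columns**, per affected subject who has no other qualifying AE in the column concerned (1/16 = 6.25%):

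| How the AE is handled | BI column | BI + Microgynon column |
|---|---|---|
| Combination only | 6.25 points too low | 6.25 points too high |
| Both phases | correct | 6.25 points too high |
| BI only, by a rule in text not seen | correct | correct |

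SAP Section 7.8.1 plans a table of non-serious AEs with an incidence above 5%. One subject exceeds that limit for any column size up to 19 (1/19 = 5.26%), but not at 20 (1/20 = 5.0%). A single AE in the window can therefore decide the column in which the event appears.

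The documents give no AE rate for these 48 h, so an expected number of affected subjects cannot be stated.

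**The case against.** **The answer may lie in text we cannot see.** The AE limits of the BI 409306 phase are blacked out. The SAP also points elsewhere: "For detailed information on the handling of the treatments in the O*C views refer to Technical TSAP analysis data set (ADS) plan", and to sponsor guidance on summarising AEs. A precedence rule could sit in any of these, so the consequence is less certain than the overlap. The combined-phase bullet itself reads as complete, though. Restoring the BI 409306 limits would not by itself repair it: a start on Day 29 creates the overlap, and a start on Day 31 puts the AEs under the wrong treatment.

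**The direction is already clear.** SAP Section 7.8 follows the protocol, SAP Section 4 declares no changes, and the label for Day 29 is BI. A careful programmer might well assign these AEs to BI. This supports the fix, but it does not remove the conflict with the written interval.

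**It may be deliberate.** On Days 29 to 31 subjects are still within the Microgynon REP, and AEs in the REP count as on treatment. The vital-signs and laboratory list likewise lets its second Microgynon phase run to the end of the REP with no visible cut at Day 29. This is the best argument for leaving the text alone. Against it, the AE bullet directly above does stop at the next treatment, and keeping the combined label would take the first 48 h after R1 out of the BI column or count them twice.

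**The consequence is small.** This stands. Safety is descriptive, AEs are also listed individually, and with 16 subjects any single-subject event passes 5% in any column. The SAP does not say whether that incidence is per column or overall.

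**Conclusion.** The point holds and is minor. The 48 h overlap follows directly from the documents, provided the last Microgynon dose is taken on Day 21 as scheduled and the REP is counted in hours from that dose. What happens to an AE in that window is open, because the limits of the BI 409306 AE phase and the ADS plan were not available. Confidence is therefore high for the overlap and moderate for its consequence.

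The 6.25 points per affected subject assume 16 subjects in each column; dropouts or replacements would change the figure. PK analyses are not touched. The BI total and the on-treatment total are not changed by the overlap either, because both cover the combined phase and the BI-alone phase.

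**What to change.** In the AE list of SAP Section 6.1, end the BI 409306 + Microgynon phase at the end of the 10-day Microgynon REP or at the administration of BI 409306 alone, whichever comes first. State that AEs starting from R1 onward are assigned to the BI 409306 phase. Subjects who do not receive R1 keep the REP end. Align the ADS specification.

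If the BI 409306 REP, which is not visible, is shorter than 48 h, also state that AEs up to the end of the Microgynon REP remain on treatment, as SAP Section 7.8.1 already implies. The totals then stay as they are. No change to the vital-signs and laboratory phases is requested here.

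The cost is one clause in one bullet and the matching ADS entry. The downside is that a late Microgynon AE starting between R1 and the end of the Microgynon REP on Day 31 would be shown under BI. It would still be visible in the AE listings and in the causality assessment. The change affects analysis labels only.

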**1.2 DRUG PROFILE**

## 1.2.2 Microgynon® (ethinylestradiol + levonorgestrel)

### Ethinylestradiol

Ethinylestradiol (EE) is a synthetic estrogen with actions similar to those of estradiol. It is frequently used as the estrogenic component of combined oral contraceptives; a typical daily dose is 20 to 40 µg. Ethinylestradiol is also used as an emergency contraceptive drug combined with levonorgestrel or norgestrel. A combined preparation of ethinylestradiol with the anti-androgen cyproterone is used for the hormonal treatment of acne and hirsutism, particularly when contraception is also required. Ethinylestradiol has also been used for hormone replacement therapy; doses of 10 to 20 µg daily are given (with a progestogen in women with a uterus), but natural estrogens are usually preferred. Ethinylestradiol is also used for the treatment of female hypogonadism and the palliative treatment of prostate cancer and malignant breast cancer.

The adverse effects of estradiol and other estrogens are related, in part, to dose and duration of therapy, and to the sex and age of the recipient. In addition, adverse effects may be modified by administration of progestogen in combined oral contraceptives or hormone replacement therapy. Whether adverse effects of natural and synthetic estrogens differ, and whether the route of administration has an effect, is less clear. The use of estrogens in girls may cause premature closure of the epiphyses resulting in decreased final adult height. Large doses of estrogens used in palliative care have also been associated with nausea, fluid retention, venous and arterial thrombosis, and cholestatic jaundice. In men, large doses of estrogen cause impotence and feminising effects such as gynaecomastia. In women, uterine bleeding may occur after the cessation of estrogen therapy.

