##### **Treatment period**

Visit 3 follows directly after the run-in-period. Subjects will be treated as below.

1 tablet of Microgynon® QD with 240 mL water on Days 1 to 17 (R2 on Day 17)  
1 tablet of BI 409306 and 1 tablet of Microgynon® with 240 mL water on Day 18 (T1 and T2)  
1 tablet of Microgynon® QD with 240 mL water on Days 19 to 21  
1 tablet of BI 409306 with 240 mL water on Day 29 (R1)

Period	Screening	Run-in	Treatment						End of Trial
Visit	1	2	3						4
Day	-70 to -29	-49 to -1	1 to 16	17	18	19 to 21	...	29	33 to 35
BI 409306					X			X	
Microgynon®		X*	X	X	X	X			

\* depending on the subjects' actual menstruation cycle. No Microgynon® on the Days -7 to -1.

An overview of all relevant trial activities is provided in the [Flow Chart](#). For visit schedule and details of trial procedures at selected visits, refer to [Sections 6.1](#) and [6.2](#), respectively.

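### SAP 6.1 keeps adverse events in the combination phase to Day 31, while laboratory and vital-sign data return to a Microgynon phase a redacted interval after the BI 409306 dose

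*SAP*

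**What the plan says.** Protocol 7.3.3 assigns both measurements and AEs to treatments "based on the actual treatment at the planned time of the measurement or on the recorded time of AE onset", and leaves the exact intervals to the SAP. SAP section 4 declares no change to the planned analysis.

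SAP 6.1 then gives two phase lists.

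- **AEs.** The only Microgynon phase runs from the first tablet "until the time of first administration of BI 409306 or last intake of Microgynon® + Microgynon® REP (10 days), whatever occurs earlier". The next phase is "BI 409306 + Microgynon® treatment (ranging from the first administration of BI 409306 + Microgynon® until end of Microgynon® REP (10 days". After that come BI 409306 alone and its follow-up.
- **Laboratory values and vital signs.** The combination phase is "BI 409306 + Microgynon® treatment (ranging from first administration of BI 409306 + Microgynon® until administration of BI 409306" plus an interval that is blacked out. A further phase follows: "Microgynon® treatment (ranging from end of until last intake of Microgynon® + Microgynon® REP (10 days". Its starting point is partly blacked out. BI 409306 alone comes after it.

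The AE summary tables in CTR Section 15.3 also carry a Total BI column, defined as "a total over all on treatment phases involving BI", so the combination phase feeds it.

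The dosing in protocol 3.1 is "1 tablet of BI 409306 and 1 tablet of Microgynon® with 240 mL water on Day 18 (T1 and T2", then Microgynon alone on Days 19 to 21, no trial drug on Days 22 to 28, and BI 409306 alone on Day 29.

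**The concern.** One section of the SAP applies a single protocol rule in two ways and gives no reason. For laboratory and vital-sign data, the period after the single Day 18 dose of BI 409306 returns to Microgynon. For AEs it never does, so an event starting well after that dose is still shown as a combination event and enters Total BI.

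The same kind of time is also labelled differently within the AE tables. The pill-free week in the run-in (Days -7 to -1) falls under Microgynon, while the pill-free week after Day 21 falls under the combination. The two sets of tables can disagree on a single finding as well. A Day 29 pre-dose laboratory abnormality (670:00, which is 262 h after the Day 18 dose) would sit under Microgynon in the laboratory table if the BI 409306 REP is shorter than 262 h. Reported as an AE with onset at that sample, it would sit under BI + Microgynon.

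The description of combination safety is at stake. SAP 7.8.1 bases all AE analyses on subjects with events, and no exposure adjustment is visible, so lengthening a phase can only add subjects to its column. With 16 subjects, one subject moves a column by 1/16 = 6.25 percentage points. The BI + Microgynon column also goes into the registry display.

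**Working it through.** The documents give no figure to reproduce. The check is a timeline.

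**Inputs**
- Day 18 combined dose at 408:00, last Microgynon tablet on Day 21 at 480:00, Day 29 BI 409306 dose at 672:00 (protocol Flow Chart). These agree with (Day - 1) x 24: 17 x 24 = 408, 20 x 24 = 480, 28 x 24 = 672.
- Microgynon REP: 10 days = 240 h (protocol 5.2.2.2, SAP 6.1).
- BI 409306 REP: blacked out, so a range of 1 to 10 days is assumed.

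**Length of the AE combination phase as written**
- End = 480 + 240 = 720:00, which is Day 31.
- Length = 720 - 408 = 312 h, or 13 days.
- Time before the Day 29 dose = 672 - 408 = 264 h, or 11 days.
- Overlap with BI 409306 alone = 720 - 672 = 48 h. This takes the BI-alone AE phase to start at the Day 29 dose, as it does in the laboratory and vital-sign list. No visible rule says which phase takes precedence.
- The second Microgynon phase in the laboratory and vital-sign list also ends at 720:00, so it has the same 48 h overlap.

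**Time labelled combination for AEs but Microgynon under the other list**

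Hours affected before Day 29 = 264 - REP; share = (264 - REP)/264.

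| Assumed BI 409306 REP | Hours affected | Share of 264 h |
|---|---|---|
| 1 day (24 h) | 240 | 91% |
| 3 days (72 h) | 192 | 73% |
| 5 days (120 h) | 144 | 55% |
| 7 days (168 h) | 96 | 36% |
| 10 days (240 h) | 24 | 9% |

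**Which days these are**

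A 72 h REP ends at 408 + 72 = 480:00, the time of the Day 21 tablet. From there up, nothing before that tablet is affected, and the affected time is mainly the drug-free Days 22 to 28 (7 x 24 = 168 h, 64% of 264 h). Days 19 and 20 come in only if the REP is shorter than about 3 days.

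**Whether redaction could explain the difference**

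The AE combination entry is intact and closes at the end of the Microgynon REP. A second Microgynon AE phase hidden by redaction would have no room before Day 29. The start of the second laboratory and vital-sign Microgynon phase is partly lost, so placing it at the end of the BI 409306 REP is an inference, though the surviving words support it.

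**The case against.** The best defence has four parts.

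- **The protocol delegates the intervals.** Section 7.3.3 hands the detail to the SAP, and section 5.2.2.2 counts all AEs through the Microgynon REP as on treatment. Both are true. But being on treatment does not make an event a combination event, and the delegation does not explain two different answers under one rule.
- **The wide window is conservative.** AEs can start late, and keeping them with the investigational drug cannot hide a signal. This would be a reasonable argument if the SAP made it. The SAP does not, and its own laboratory and vital-sign split goes the other way. It also leaves the 48 h overlap unresolved.
- **The columns are not comparable anyway.** The first Microgynon phase lasts 45 to 66 days (from Day -28 or Day -49 to Day 18), against 11 days from the combined dose to Day 29. This stands. Aligning one boundary corrects the labels but does not equalise exposure.
- **Materiality is modest.** Safety is descriptive in an exploratory trial of 16 subjects, AEs are listed individually, and drug-related AEs have their own table. This also stands and limits the weight of the point.

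A reader might infer that all of Days 19 to 21 is misassigned. The documents do not support that, because the BI 409306 REP is redacted and a REP of 3 days would place the time up to the Day 21 tablet properly in the combination phase.

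A reader might also infer that withdrawal bleeding on Days 22 to 28 will inflate the BI 409306 figures. The protocol ties withdrawal bleeding to the run-in pill-free week. On stopping estrogen it says only "In women, uterine bleeding may occur after the cessation of estrogen therapy", and nowhere does it say that an expected bleed will be recorded as an AE. The overstatement is a possibility, not a demonstrated effect.

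**Conclusion.** The inconsistency is real and rests on visible text. SAP 6.1 applies two definitions of the combination phase under one protocol rule. The AE version counts events that start after the BI 409306 REP and before Day 29 under BI + Microgynon and Total BI, and as written it overlaps the BI-alone phase by 48 h.

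The size depends on the redacted REP and ranges from 91% of the 264 h at 1 day to 9% at 10 days. The planned follow-up phase after BI 409306 hints at a short REP, since the end-of-trial visit on Days 33 to 35 comes only 4 to 6 days after the last dose. This is an inference: the laboratory and vital-sign list also allows the BI-alone phase to end at that visit. These shares are of time, and the documents give no basis for turning them into AE counts.

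The consequence is that the AE incidence attributed to BI 409306 can be overstated in the descriptive safety tables. The pharmacokinetic endpoints and their confidence intervals are unaffected. The point should be corrected, but it does not threaten the trial's objective.

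**What to change.** In SAP 6.1, give AEs the split used for laboratory values and vital signs:

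1. End the BI 409306 + Microgynon phase at the Day 18 dose plus the BI 409306 REP.
2. Assign later AEs to Microgynon until the end of the Microgynon REP or the next BI 409306 dose, whichever is earlier.
3. Leave that second Microgynon phase out of Total BI.
4. Apply the same cut at the Day 29 dose to the laboratory and vital-sign list.

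The cost is SAP wording and one more phase boundary in the AE dataset. It should not be assumed that this boundary is already programmed: SAP 6.1 refers dataset handling to a separate technical plan that is not among the documents. The downside is that late-onset AEs after the BI 409306 REP leave the BI columns, although they remain in the AE listings. If the sponsor wants the wider AE window on purpose, the SAP should give the reason and still settle which phase takes precedence from Day 29.
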